We have developed directly labeled fluorescent PPS to enumerate and characterize PPS-specific B cells. This allowed the analysis of antigen-specific B cell responses to pneumococcal vaccination. The results of these studies demonstrated that the immune response to PPV in young adults consists predominantly of IgM memory B cells [16]. In contrast, in the elderly who are deficient in memory B cells, particularly IgM memory B cells [17], the predominant B cell phenotype in response to PPS consists of switched memory B cells (IgG/A+IgM-CD27+)[18]. HIV+ individuals, are also deficient in CD27+IgM+ B cells yet the predominant response consists of PPS-specific CD27+IgM+ B cells [19-22], albeit at significantly reduced numbers. Thus, the cause of poor pneumococcal vaccine responses varies according to study population. Several investigators and our preliminary data show that like the elderly and HIV-positive, absolute number and percentage of memory B cells are significantly lower in stable RT recipients, at 6 months to 5 years post-RT, compared to healthy subjects [23, 24]. Moreover, low number and percentage of IgM memory B cells correlate with poor antibody responses to PPV23.

This may however not be the only cause for poor vaccine responses. The ability to isolate antigen-specific B cells allows us to explore other deficits and/or changes in surface markers and gene expression potentially implicated in poor vaccine responses. It has been well described that members of the TNFR family and

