8	BIK	BCL2-interacting killer	Pro-apoptotic function	37	LCP2	Lymphocyte cytosolic protein 2	B cell receptor signaling
9	TNFSF15	Tumor necrosis factor alpha	Activates NFkB and MAPK, promotes activation of caspases and apoptosis	38	GCET2 (GCSAM)	Germinal center associated signaling and motility	B cell signaling and motility
10	Siva1	Siva 1 apoptosis inducing factor	CD27 binding protein, pro-apoptotic	39	CD38	CD38 molecule	Signal transduction
Cytokines and receptors				40	NT5E	5' nucleotidase ecto	CD73; promotes class switching exonucleases
11	IL-1B	Interleukin1beta	Inflammatory mediator, plays a role in cell differentiation, proliferation and apoptosis	41	CD39	CD39 molecule	Exonucleases
12	IL-6	Interleukin 6	Inflammation and maturation of B cells	42	MS4A1	Membrane spanning 4-domain A1	Plays a role in T cell independent immune response
13	IL-7	Interleukin 7	Plays a role in B cell development	Igs			
14	IL-8	C-X-C motif chemokine ligand	Chemokine, mediator of the inflammatory response	43	IgD	Immunoglobulin heavy constant delta	Effector phase of humoral immunity
15	IL-10	Interleukin 10	Immune regulator, inhibits certain cytokines; cell survival and proliferation	44	IgA	Immunoglobulin alpha Fc receptor	Mediates immune response to pathogens
16	IFN-gamma receptor	Interferon gamma receptor	Innate and adaptive immune response	Metabolism			
17	IFN-gamma	Interferon gamma	Innate and adaptive immune response	45	HKII	Hexokinase 2	Hexokinases phosphorylate glucose to produce glucose-6-phosphate (G6P)
18	TNF-alpha	Tumor necrosis factor alpha	B cell function	46	PFKP	Phosphofructokinase	Catalyzes conversion of fructose 6-phosphate to fructose 1,6-bisphosphate
19	TLR1	Toll like receptor 1	Innate immune response	47	ENO1	Enolase 1	Glycolytic enzyme
20	CCR2	C-C motif chemokine receptor 2	Mediates chemotaxis	48	PGAM	Phosphoglycerate mutase	Enzyme that catalyzes step 8 in glycolysis
Transcription factors				49	LDHA	Lactate dehydrogenase A	Enzyme that catalyzes the inter conversion of pyruvate and L-lactate with interconversion of NADH and NAD+
21	IRF4	Interferon regulatory factor 4	Lymphocyte specific transcriptional activator that regulates TLR signaling	51	COXII	Cytochrome c oxidase subunit 2	Component of respiratory chain
22	BACH2	BTB domain and CNC homolog 2	Transcriptional repressor, expressed through B cell differentiation; major target Blimp1=Prdm1	52	CPT1	Carnitine palmitoyltransferase 1 a	Mitochondrial oxidation gene

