Statistical Analysis Plan and Sample Size Justification for Aim 3

Aim 3 will examine differences in expression of TNFR markers (TACI, BCMA, and BAFF-R) using single cell qPCR on a subset of 10 participants (5 responders and 5 non-responders) from each of the 5 groups described in Aims 1 and 2 evaluated at baseline and 7 days post-vaccination. Single cell qPCR allows us to not only evaluate differences in expression between groups but also allows us to estimate the within subject and within group heterogeneity with great precision. Each participant sample provides between 40-96 viable cells that will be evaluated for gene expression at the single cell level. Relative fold-change in expression between participants who are 65-75 RT, 35-45 RT, or 65-75 DM/HTN with respect to the relevant controls will be evaluated using a linear mixed model approach. The model will include fixed effects for participant group, response status, and time and a random subject effect to account for repeated measurements resulting from individual cells from the same subject samples. Comparisons of number of gene expression between groups and within group between times will be evaluated using a series of contrasts from the LMM. For comparisons within group between responders and non-responders, a sample size of 5 responders and 5 non-responders with ≥ 40 cell level measures at 2 time points provides 80% power to detect 2.7 fold-increase or a 0.60 fold-decrease in expression using a two-sided test assuming within subject correlation of 0.5 and a Bonferroni corrected significance level (up to 10 comparisons) of $p = 0.005$. For comparisons between groups, we will have 10 subjects per group allowing us to detect even smaller fold-changes in expression.

All electronic data will be kept on the VA secure V drive or R drive and on MUSC secure Z drive that only team members will have access to.

13.0 Provisions to Monitor the Data to Ensure the Safety of Subjects (if applicable)

All adverse events (AE) will be reported and monitored through the data safety monitoring plan. The AE's will be characterized by: intensity/severity; expectedness; relatedness; frequency; outcome; treatment or action taken.

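### Aim 3's single fold-change model makes no provision for cells with no detectable transcript, so its result can turn on an unstated handling of non-detects

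*Combined protocol and SAP*

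**What the plan says.** Section 12.0, Aim 3, takes 10 participants per group (5 responders, 5 non-responders), sampled at baseline and day 7. The measurement unit is the cell: "Each participant sample provides between 40-96 viable cells that will be evaluated for gene expression at the single cell level". Relative fold-change "with respect to the relevant controls will be evaluated using a linear mixed model approach". On its terms: "The model will include fixed effects for participant group, response status, and time and a random subject effect to account for repeated measurements".

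The power statement covers fold-change only. For the responder comparison within a group, with at least 40 cells per sample, the design "provides 80% power to detect 2.7 fold-increase or a 0.60 fold-decrease in expression using a two-sided test assuming within subject correlation of 0.5". The level is 0.005 after Bonferroni correction.

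The Aim 3 text gives no detection limit, no rule for dropping or imputing a cell without signal, no analysis of the share of expressing cells, and no two-part or censored model. One unclear sentence refers to a number in connection with gene expression, but tests it by contrasts from the same model. The line on graphical checks and possible transformations belongs to the Aims 1 and 2 text.

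Section 4.0 makes gene expression (56 genes) a secondary endpoint. Specific Aim 3 in Section 1.0 also plans flow cytometry, for which the Aim 3 analysis text gives no method.

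**The concern.** A cell in which a gene is not detected has no log expression value, so the analyst must choose what to do with it. If such cells are dropped, the model compares only expressing cells, and a group with fewer expressing cells looks the same as one with more. If they are given a floor value, the estimated fold-change is partly a function of that floor and merges two quantities: how many cells express the gene, and how strongly. A transformation does not remove a spike of identical values.

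The plan's own content makes this foreseeable for part of the panel. Table 4 in Section 10.0 lists IgD ("Immunoglobulin heavy constant delta"). Section 2.0 reports that the response to the polysaccharide vaccine is mainly IgM memory cells in young adults, but in the elderly mainly "switched memory B cells (IgG/A+IgM-CD27" positive). The share of cells with an IgD transcript could therefore plausibly differ by age group, one of the study's main contrasts.

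At stake is whether an Aim 3 fold-change can be interpreted, and compared between groups whose detection rates differ.

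**Working it through.** **1. The plan's own figure.** Alpha: 0.05/10 = 0.005, which agrees. Detectable difference for 5 versus 5 subjects, 40 cells, correlation 0.5:

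- variance of a subject mean, in units of total variance: v = 0.5 + 0.5/40 = 0.5125
- normal approximation: (2.807 + 0.842) × √(2 × 0.5125/5) = 3.649 × 0.453 = 1.65 SD
- noncentral t, 8 df: 2.20 SD

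Since log2(2.7) = 1.43, a 2.7-fold increase implies a log2 SD of 1.43/1.65 = 0.87 (normal) or 1.43/2.20 = 0.65 (t). The documents give no SD, so the figure cannot be confirmed. One SD also does not yield both stated limits if 0.60 is a ratio, because the mirror of 2.7 is 1/2.7 = 0.37. For this point, what matters is that the calculation has no term for the share of cells expressing.

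**2. Illustration, all values assumed.** Two groups at one time point; 60 cells per subject; mean 5 log2 units among expressing cells in both groups; cell SD 1; between-subject SD 0.5 on log2 expression and 0.6 on the logit of the share; alpha 0.005. Tests are t tests on subject-level summaries. With balanced cell counts this matches the random-intercept contrast; with cells dropped it approximates it.

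| Scenario | Detected cells only | Test of share |
|---|---|---|
| 60% v 30%, 10 v 10 | about 0.5% | about 83% |
| 60% v 30%, 5 v 5 | – | about 30% |
| 60% v 40%, 10 v 10 | about 0.5% | 36% |
| 95% v 85%, 10 v 10 | 0.4% | 62% |

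**3. Fill-in.** The log2 difference is (difference in average share) × (5 − floor). Averaging over the between-subject variation, nominal shares of 60% and 30% become 59.3% and 31.3%, a difference of 0.279. Nominal 95% and 90% become 94.2% and 88.7%, a difference of 0.055.

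| Floor (log2) | 60% v 30%: log2 difference → fold-change | 95% v 90%: log2 difference → fold-change |
|---|---|---|
| 0 | 0.279 × 5 = 1.40 → 0.38 | 0.055 × 5 = 0.27 → 0.83 |
| 2 | 0.279 × 3 = 0.84 → 0.56 | 0.055 × 3 = 0.16 → 0.89 |
| 4 | 0.279 × 1 = 0.28 → 0.82 | 0.055 × 1 = 0.05 → 0.96 |

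For 60% versus 30% at 10 versus 10, the filled-in model rejects 80%, 71% and 19% of the time at floors 0, 2 and 4.

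**4. Share and level moving in opposite directions.** A second simulation used 40 cells, log2 SD 0.65 (which gives 80% power for 2.7-fold at 5 versus 5 when every cell expresses) and logit SD 0.5. Let the 30% group also have a true 2.7-fold higher level in expressing cells. The single-model estimate is 2.70 if non-detects are dropped, 0.92 if they are filled in 2 log2 units below the reference group's expressing mean, and 0.19 at 10 units below. Even the direction depends on the choice.

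**5. Raw scale.** The plan does not state the scale. On the raw scale zeros can enter without a floor. Under the assumptions of step 4, but with equal level, 60% versus 30% then gives a ratio of 0.52 and rejection of 49% (10 versus 10) or 13% (5 versus 5). Share and level remain merged.

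**The case against.** Several limits stand.

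- **Detection rates are unknown.** A reader might infer that non-detection is certain to affect TACI, BCMA and BAFF-R. The documents do not support that. The Aim 3 statistical text names those three markers and gives no detection rate for them; the isotype example comes from the wider Table 4 panel. That table's IgA row is titled as an Fc receptor, so only IgD serves as the example, and the cell-type statement is background from earlier work.
- **The model is not blind to share.** A reader might also infer that it can never register a difference in the share expressing. That holds only if non-detects are dropped. With a low floor the same model often rejects (80% and 71% above). It then fails to separate share from level.
- **The aim does not draw this distinction.** The aim concerns receptor expression; nothing in the documents singles out fewer positive cells versus less per cell as its question. Flow cytometry could show receptor-positive cells at protein level, which helps in part, although no analysis of it is specified.
- **The illustration is chosen.** The 0.5% rejection follows by construction, since no difference in level was simulated. A floor of 4 is high for a detection limit: with total SD √(1 + 0.25) = 1.12, about 19% of expressing cells would lie below it. At 95% versus 90% the fold-changes stay between 0.83 and 0.96.

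None of this supplies the missing rule. The gap remains, and its size depends on the gene.

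**Conclusion.** The concern holds in a bounded form. The only analysis named for the single-cell data has no component for, and no rule on, cells without detectable transcript. Where non-detection is appreciable, the reported fold-change is either silent on the share expressing or set partly by an arbitrary floor. In the illustration that means about 0.5% rejection against about 83% for a direct test of the share, and fold-changes from 0.38 to 0.82 from the same data. Where nearly all cells express the gene, the effect is small. These sizes rest on assumed shares, SDs and cell counts; the documents give only 40 to 96 cells per sample. The change should be made because it is cheap and must precede the group comparisons. A reader should not infer a threat to the main results: the endpoint is secondary, and the Aim 1 and 2 primary outcomes are untouched.

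**What to change.** Before any group comparison, set the detection cut-off and replace the single model with a two-part analysis per gene:

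1. share of cells expressing, by logistic mixed model or subject-level logit;
2. log2 expression among expressing cells, by linear mixed model.

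Each part keeps the plan's group, response status and time terms and a random subject effect. Report both parts.

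Use small-sample tests (subject-level t tests or corrected denominator degrees of freedom), with a stated split of alpha between the parts. Do not rely on an asymptotic 2-df likelihood-ratio test: simulated without a group difference, at nominal 0.5% it rejected about 1.8% of the time at 5 versus 5 and 0.9% at 10 versus 10.

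The cost is SAP wording and standard software, with no new samples. Some power is lost to the split. Under the assumptions of working step 4 with equal level, power for a 60% versus 30% share falls from 91% at alpha 0.005 to 85% at 0.0025 with 10 versus 10, and from 37% to 26% with 5 versus 5. The plan should state that responder versus non-responder comparisons within a group have low power for share differences, and should give the SD and shares assumed for each part.

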We will measure TNFR expression by B cells following immunization with PCV13 in 65-75 year old RT and compare them to each of the groups described in Specific Aim 1. Gene expression, with focus on the B cell activating factor (BAFF) system, will be measured in PPS-specific and non-PPS specific B cells using single cell genomics and flow cytometry. These measures will be correlated with post-immunization functional antibody activity, a surrogate of protection.

Our central hypothesis is that the aging RT population responds poorly to PCV13 vaccination reflecting the combined effects of aging and RT. We postulate that both the number of memory B cells and expression of tumor necrosis factor (TNF) superfamily receptors, which play crucial roles in the response to pneumococcal polysaccharides (PPS), are deficient in the elderly RT population and contribute to poor pneumococcal vaccine responses.

We have developed fluorescently labeled PPS allowing us to study the nature and surface receptors of PPS-specific B cells. Our preliminary data demonstrate that RT recipients 1. Respond poorly to pneumococcal immunization as measured by antibody titer and functional antibody activity. 2. RT recipients and healthy elderly have lower absolute number of both IgM and switched memory B cells. 3. The number of PPS-specific IgM and switched memory B cells are significantly lower in RT recipients and 4. TACI and BAFF-R, members of the TNF superfamily receptors, expression is significantly lower in the PPS-specific memory B cells in the RT population versus healthy controls. The overall objective of this proposal is to characterize the immune response and explore possible mechanisms of poor vaccine responsiveness following immunization with PCV in the rapidly growing group of elderly with RT. As the RT population is a

heterogeneous group we will study only those in whom the underlying cause of renal failure is diabetes mellitus type 2 (DM2) and/or hypertension (HTN).

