10.0 Study Design / Methods

The overall objective of this proposal is to characterize the immune response and explore possible mechanisms of poor vaccine responsiveness following immunization with PCV in the rapidly growing group of elderly with RT. As the RT population is a heterogeneous group we will study only those in whom the underlying cause of renal failure is diabetes mellitus type 2 (DM2) and/or hypertension (HTN). There will be 5 study groups as outlined above.

Volunteers from all 5 study groups will be recruited as above. All individuals from study groups 1-4 who meet the study criteria will receive Prevnar13[®] on day 0. Group 5 volunteers will be recruited during the first year of the study and those who have not previously received PPV23 will receive PPV23 on day 0 and PCV13 on day 366. Blood samples will be obtained as outlined below and results obtained in various groups will be compared.

Timing of blood samples

Peripheral blood samples will be collected at day 0 (pre-immune), day 7, and day 30 (4 weeks post-PPV23) for groups 1-4 and at days 366, 373 and 396 for group 5. In addition, day 5, and 10 blood samples will be obtained from a limited (n=10) number of elderly RT participants to determine the optimal time point for circulation of PPS-specific B cells. Yearly blood samples will be obtained thereafter for serum antibody and OPA analyses to test longevity of antibody and OPA responses. Samples from days 0, 30 and yearly samples will be used for antibody titers and opsonophagocytic assays. Samples from day 0 (day of vaccination with PCV13) and day 7 will be used for flow cytometric analysis. The day 7 time point for isolation of antigen-specific B cells was specifically chosen as we have extensively studied temporal dynamics of antigen-specific B cell in peripheral blood samples (unpublished studies) and have found that the highest number of antigen-specific B cells are present in the peripheral circulation at day 6 and 7 with rapid (70+%) decline at day 8 in healthy young, elderly including those with DM2 and HTN, and HIV-positive. At day 30, a minimal number of PPS-specific B cells were present. Others have described similar findings [28, 29].

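### As written, the Aim 3 single-cell model has no term for cell kind, so an effect confined to PPS-specific B cells is diluted and cross-age contrasts may partly reflect cell mix

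*Combined protocol and SAP*

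**What the plan says.** Section 12.0 (Aim 3) makes the single cell the unit of observation: "Each participant sample provides between 40-96 viable cells that will be evaluated for gene expression at the single cell level". On the model it states: "The model will include fixed effects for participant group, response status, and time and a random subject effect". Comparisons "between groups and within group between times will be evaluated using a series of contrasts from the LMM".

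Section 1.0 (Specific Aim 3) says that gene expression "will be measured in PPS-specific and non-PPS specific B cells using single cell genomics and flow cytometry". The same section reports preliminary data in which TACI and BAFF-R expression was lower in the PPS-specific memory B cells of transplant recipients than in healthy controls. Its central hypothesis treats memory B-cell number and TNF-receptor expression as two separate deficits.

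On cell mix, section 2.0 says that "the immune response to PPV in young adults consists predominantly of IgM memory B cells", whereas in the elderly "the predominant B cell phenotype in response to PPS consists of switched memory B cells". The documents do not say how cell kind enters the Aim 3 analysis, or how many cells of each kind are taken from each sample.

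**The concern.** Aim 3 asks whether receptor expression per cell is deficient in older transplant recipients. A model with group, response status and time as its only fixed effects compares averages over whatever cells were assayed. Two things follow.

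- **Dilution.** If the deficit lies only in PPS-specific cells, where the preliminary data put it, every non-PPS-specific cell in the fit pulls the estimate towards no difference.
- **Composition.** If two groups contribute different shares of cell kinds, and the kinds differ in expression, the contrast is non-zero even when expression within each kind is the same. The random subject effect does not remove a shift shared by a whole group. Aim 3 could then report as an expression deficit something that belongs to cell number, which Aim 2 already addresses.

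**Working it through.** **The plan's own figures.** The Bonferroni level reproduces: 0.05/10 = 0.005. The detectable fold-changes (2.7 and 0.60) cannot be reproduced, because no standard deviation is given. Below, 0.60 and 2.7 serve only as example effect sizes.

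**Inputs.** From section 12.0: the model terms, at least 40 cells per sample, within-subject correlation 0.5 and 10 participants per group. Assumed, because the documents do not give them: the share of PPS-specific cells, the IgM/switched split, and the ratio R of expression between kinds. Calculations are on the log scale.

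**Dilution.** Let a share s of the cells be PPS-specific in both groups, with the effect in those cells only. Then apparent fold = (true fold)^s.
- s = 0.75: 0.60^0.75 = 0.68
- s = 0.50: 0.60^0.50 = 0.77, and 2.7^0.50 = 1.64
- s = 0.25: 0.60^0.25 = 0.88

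**Composition, cross-age contrast.** With no true difference within either kind, apparent fold = R^(difference in share).
- Shares 0.3 versus 0.7: R = 2 gives 2^-0.4 = 0.76; R = 3 gives 0.64; R = 4 gives 0.57.
- Shares 0.4 versus 0.6: R = 2 gives 2^-0.2 = 0.87; R = 3 gives 0.80; R = 4 gives 0.76.
- R = 1, or equal shares, gives 1.00.

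A simulation of the between-group contrast used 4,000 runs, 10 subjects per group, 40 cells each, an assumed between-subject SD of 0.4 and cell SD of 0.6 on the ln scale, and alpha 0.005. With no per-cell difference and no cell-kind term, it rejected in 7% of runs for R = 2 with shares 0.3 versus 0.7, 24% for R = 3 with the same shares, and 1.4% for R = 2 with shares 0.3 versus 0.5. With adjustment for kind, rejection was 0.4% to 0.6%.

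**Price of stratifying.** If 0.5 is the correlation between cells of one subject, the variance of a subject mean is proportional to 0.5 + 0.5/m for m cells.
- 20 instead of 40 cells: 0.525/0.5125 = 1.024, a rise of 2.4%.
- 40 cells split six ways (two PPS classes by three subsets, about 6.7 cells each): 0.575/0.5125 = 1.122, a rise of about 12%.

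**The case against.** The best reply is that pooling is inferred. Section 1.0 names two cell populations, and one model for each would be consistent with the text. That is fair: section 12.0 never says outright that both kinds enter one fit. But it describes a single model and lists its terms, and the literal reading pools. Separate fits would remove the dilution, but would still leave the IgM/switched mix free within PPS-specific cells.

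Three stronger readings are tempting but not supported.

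- **That all the groups are known to differ in cell mix.** The IgM/switched contrast in section 2.0 is between young and elderly, and the young result followed PPV, not PCV13. For transplant recipients, section 1.0 says that "The number of PPS-specific IgM and switched memory B cells are significantly lower in RT recipients", which is a count of both subsets and not their ratio. Section 2.0 does report a lower percentage of memory B cells in stable recipients than in healthy subjects. It gives no figure or age matching, and nothing on the PPS-specific or IgM/switched share of the assayed cells.
- **That vaccination is shown to change the mix from day 0 to day 7.** Section 10.0 says that the "highest number of antigen-specific B cells are present in the peripheral circulation at day 6 and 7". This too is a number; if cells are sorted on PPS binding, it does not set their share of the assayed cells.
- **That mix alone can pass the plan's 0.60 detectable limit.** Section 12.0 gives that limit for 5 responders versus 5 non-responders within a group. For between-group contrasts it gives no figure, only that smaller changes are detectable.

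It is also true that composition is measured in Aim 2 at days 0 and 7, so it is available for interpretation. Subset at day 7 may itself be part of the vaccine response, which makes the unadjusted average a legitimate quantity to report. Neither point tells the reader which cells the Aim 3 contrast describes.

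**Conclusion.** The point holds for the model as written: its contrasts are averages over cell kinds, while the hypothesis concerns PPS-specific memory cells. Dilution is the firmer part. It needs only that non-PPS-specific cells are pooled and that the effect is confined to, or larger in, PPS-specific cells. It vanishes if the effect is the same in both kinds. The composition effect is documented as a possibility for cross-age contrasts only. It is zero if the sampled mix is equal or expression does not differ by kind. For day 0 versus day 7, and for transplant recipients versus age-matched controls, a shift in mix is plausible but not documented as a proportion of the assayed cells.

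Every size given here rests on assumed shares and ratios. Gene expression is a secondary endpoint (section 4.0) studied in 10 participants per group, and the antibody, OPA and B-cell-number endpoints are unaffected. This should be fixed, but it does not put the trial's main results at risk.

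**What to change.** Before the single-cell data are analysed, amend the Aim 3 part of section 12.0 to:

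1. Keep the flow-sort label with every cell, and state how many cells of each kind are planned per sample.
2. Add PPS-specificity (yes/no) with its interactions with group and time, or pre-specify separate models for PPS-specific and non-PPS-specific cells.
3. Name the contrast in PPS-specific cells as the main Aim 3 contrast, with non-PPS-specific cells reported beside it.
4. Report an estimate adjusted for IgM/switched subset, or standardised to a common subset mix, as a supporting analysis next to the unadjusted average.

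The cost is SAP wording, one label per cell and fewer cells per stratum. Splitting on PPS-specificity alone costs little if the split is roughly even. The six-way split costs more, and some strata may be sparse or empty, which is a further reason to keep subset adjustment in the supporting role. Both variance figures assume that the plan's 0.5 is a cell-to-cell correlation; the SAP should say whether it is.
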